8.6 Description of Additional Subgroups to Be Analyzed

To determine consistency of immunogenicity across various subgroups in Phase 1/2/3a and Phase 3c, the immunogenicity and the 95% CIs may be estimated using similar methods to the primary analyses for groups stratified by the following classification variables, if feasible:

- Seropositive or seronegative by SARS-CoV-2 nucleocapsid antibody test on or prior to Day 29
- Age groups: ≥ 18 to < 60 years and ≥ 60 years
- Age and health risk for severe disease: ≥ 18 to < 60 years and “healthy,” ≥ 18 and < 60 years and “at risk,” and ≥ 60 years
- Sex (female, male)
- Race/ethnicity
- Receipt of a live non-COVID-19 vaccine within 28 days before or after any study vaccination

These subgroup analyses may also be performed for the exploratory analyses of vaccine efficacy if there are sufficient COVID-19 events to make such subgroup analyses feasible.

Safety may also be evaluated by Age group, Age and health risk for severe disease and Sex.

8.7 Statistical Analysis Methodology

Details of the statistical analyses, methods, and data conventions are described in the SAP. Statistical analysis will be performed using SAS® software version 9.4 or later. Continuous variables will be summarized using the mean, standard deviation, median, minimum value, and maximum value. Categorical variables will be summarized using frequency counts and percentages. Data will be listed in data listings.

8.7.1 General Considerations

8.7.1.1 General Considerations for Phase 1/2/3a Substudy

For Phase 1/2/3a, immunogenicity data analysis will be considered to meet the primary immunogenicity objective if the lower bound of the 95%CI for $SC^{154} > SC^{Placebo}$. This analysis will be based on the Phase 1/2/3a IAS (Section 8.1). Sensitivity analyses will be performed in the per protocol (PP) set.

Statistical analysis of safety data will be descriptive, and 95% CIs will be provided whenever applicable. It will be based on the Phase 1/2/3a and Phase 2/3a SAS and reactogenicity analysis set (RAS). Sensitivity analysis of unsolicited events will also be performed in the Phase 1/2/3a ITT and Phase 2/3a ITT analysis sets.

8.7.1.2 General Considerations for Phase 3b

Statistical analysis of safety data will be descriptive, and 95% CIs will be provided whenever applicable. It will be based on the Phase 3b safety analysis set (SAS) and Phase 3b reactogenicity analysis set (RAS). Sensitivity analysis of unsolicited events will also be performed in the Phase 3b ITT analysis set and in the Pooled SAS. Sensitivity analysis of solicited events will be performed in the Pooled RAS.

The primary efficacy analysis will be conducted in the Phase 3b mITT and will be considered to meet the primary endpoint if the lower limit of the 95% CI for VE exceeds 30%. Sensitivity analyses will be performed in the Phase 3b per protocol (PP) set and the Pooled mITT.

8.7.1.3 General Considerations for Phase 3c Substudy

Phase 3c-1 immunogenicity noninferiority data will be considered to meet the primary immunogenicity noninferiority endpoint if the lower bound of the 95% confidence interval for the geometric mean ratio of ARCT-154 / ChAdOx1 excludes 0.67. Geometric mean concentrations will be displayed in international units (i.e., using the WHO/NIBSC reference standard) if available.

A sequential/hierarchical testing procedure will be used to control type 1 error rate over the Phase 3c primary endpoint and the secondary endpoints such that the secondary immunogenicity endpoints will only be tested if the null hypothesis is rejected for the primary endpoint and the secondary endpoints numbers 1 through 5 will be tested sequentially using the same hierarchical test procedure with each endpoint only being tested if the null hypothesis is rejected for the preceding endpoint.

8.7.2 Overview of Statistical Methods: Estimation of Estimands and Sensitivity Analyses

A summary of the statistical methods and sensitivity analyses is presented in [Table 18](#).

Table 18 Summary of Statistical Methods, Including Sensitivity Analyses

Estimand Label	Estimand Description	Main Estimation			Sensitivity Analysis
		Analysis Set	Imputation/Data/Censoring Rules	Analysis Model/Method	
Estimand 1	NAb by surrogate virus neutralization test (primary for Phase 1/2/3a, NAb by PRNT50 and Bab (secondary for Phase 1 and 2 only), NAb by pseudovirus microneutralization test (MNT; secondary for Phase 3c) and BAb (secondary for Phase 1/2/3a and Phase 3c) responses at defined time points following vaccination (as defined in Sections 3.1.1, 3.1.2, and 3.3.2) with ARCT-154 or placebo. The primary immunogenicity endpoint (Phase 1/2/3a) and secondary immunogenicity noninferiority endpoints (Phase 3c) will be measured based on responses at Day 57.	Phase 1/2/3a IAS Phase 3c-1 IAS	For deaths unrelated to COVID-19, censor at date of death. For participants who undergo Switchover/Further Study Vaccine or receive a non-study vaccine, censor at date of Switchover/Further Study Vaccine or non-study vaccination. Participants with early infection (prior to Day 57) are excluded from the analysis.	Proportion of participants in each study vaccine group that demonstrate seroconversion (as defined by 4-fold increase in antibody concentration from baseline). International units (i.e., the WHO/NIBSC international reference standard) will be used if available. NAb and BAb geometric mean antibody titers/concentrations	Sensitivity: the same analysis will be performed in the Phase 1/2/3a and Phase 3c-1 PP analysis sets.

Table 18 Summary of Statistical Methods, Including Sensitivity Analyses

Estimand Label	Estimand Description	Main Estimation			Sensitivity Analysis
		Analysis Set	Imputation/Data/Censoring Rules	Analysis Model/Method	
Estimand 2	
The proportion of participants (and 95% confidence interval) with virologically confirmed COVID-19 (Appendix 2) detected after 7 days post the second study vaccine dose.Proportion of participants (and 95% confidence interval) with virologically confirmed COVID-19 detected at any time after first vaccine dose	Phase 3b mITT (primary) Phase 3c mITT (exploratory)	For deaths unrelated to COVID-19, censor at date of death. For participants who undergo Switchover/Further Study Vaccine or receive a non-study COVID-19 vaccine, censor at date of Switchover or non-study vaccination.	The proportion of participants with virologically confirmed COVID-19 (Appendix 2) in each vaccine group will be displayed together with 95% CI.	Sensitivity: the same analysis will be performed in the Pooled mITT and Phase 3b PP analysis sets.

Estimand 3	Percentage of vaccinated participants who would develop unsolicited AEs, AEs leading to discontinuation/withdrawal, MAAEs, and SAEs within timeframe up to the earlier of Day 92/Switchover/Further Study Vaccine or receipt of non-study COVID-19 vaccine. A treatment policy strategy is used for assessing safety irrespective of a current (or prior) SARS-CoV-2 infection at time of the study vaccination. See Table 17 for full definition. Events occurring before and after Switchover/Further Study Vaccine will be analyzed separately.	Phase 1/2/3a SAS Phase 2/3a SAS Phase 3b SAS Phase 3c SAS Pooled SAS	SARS-CoV-2 infections and death due to COVID-19 (if they meet the AE and time window criteria) are included in the endpoint (composite strategy).	Summaries of number of participants (%) with unsolicited AEs (including summary by severity and relatedness to study vaccine), AEs leading to discontinuation/withdrawal, MAAEs, and SAEs will be presented. The Clopper-Pearson 95% CIs will be presented for the incidence rate of these events. See Section 8.7.3.2 and the SAP for further details.	Sensitivity analyses will also be performed in the Phase 1/2/3a ITT Phase 2/3a ITT Phase 3b ITT Phase 3c ITT Pooled ITT Supportive: Analysis will be performed for different time intervals, specifically: All MAAEs, AE/SAEs, AEs leading to discontinuation/withdrawal up to Day 29, Day 57, Day 92, and Day 394 or Final Visit/Early Termination Visit/receipt of non-study COVID-19 vaccine after the first vaccination will be summarized accordingly. AEs occurring after the Day 92 will be recorded and summarized for the interval Day 92 up to Day 394 (Phase 1/2/3a and Phase 3b only). For Phase 1/2/3a and 3b, AEs in participants that do not receive additional study vaccine at Day 92 will be recorded separately for the interval
------------	--	---	---	---	---

Table 18 Summary of Statistical Methods, Including Sensitivity Analyses

Estimand Label	Estimand Description	Main Estimation			Sensitivity Analysis
		Analysis Set	Imputation/Data/Censoring Rules	Analysis Model/Method	
					from Day 92 up to Day 394 All AEs including those occurring after receipt of a non-study COVID-19 vaccination will be summarized separately as supportive analyses, if applicable.
Estimand 4	Percentage of vaccinated participants who would provide reactogenicity information within timeframe. A treatment policy strategy is used for assessing safety irrespective of a current (or prior) SARS-CoV-2 infection at time of the study vaccination. See Table 17 for full definition.	Phase 1/2/3a RAS Phase 2/3a RAS Phase 3b RAS Phase 3c RAS Pooled RAS	Events are only recorded for the initial vaccination series. SARS-CoV-2 infections and death due to COVID-19 (if they meet the AE and time window criteria) are included in the endpoint (composite strategy).	Summaries of number of participants (%) with solicited AEs (by toxicity grade) will be presented. The Clopper-Pearson 95% CIs will be presented for the incidence rate of these events. See Section 8.7.3.2 and the SAP for further details.	

Abbreviations: NAb=neutralizing antibody; Bab=binding antibody; PRNT50=plaque reduction neutralization test at 50% reduction; GMT=geometric mean titer; GMC=geometric mean concentration; AE=adverse event; CI=confidence interval; COVID-19=coronavirus disease 2019; HR=hazard ratio; MAAE=medically attended adverse event; mITT=modified intent-to-treat; PP=per protocol; RAS=reactogenicity analysis set; SAE=serious adverse event; SAP=statistical analysis plan; SARS-CoV-2=severe acute respiratory syndrome coronavirus 2; SAS=statistical analysis set

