4.5.5.2 Collection of Unsolicited Adverse Events and COVID-19 Exposure/Symptoms

Weekly and monthly phone calls and clinic visits (Section 4.5.3) including unscheduled and ET, if applicable) will be used to collect unsolicited AEs and COVID-19 exposure/symptoms:

- Unsolicited AEs will be recorded through Final Visit or ET Visit. For unsolicited AEs categorized as AEs leading to discontinuation/withdrawal, medically attended adverse events (MAAEs), and serious adverse events (SAEs) documentation will occur through 365 days after the completion of the initial vaccination series (up to Day 394).
- Symptoms of COVID-19 (Section 4.5.3.7 and Appendix 2) or exposure to SARS-CoV-2 will be recorded from first study vaccine administration throughout the entire study (Final Visit or ET Visit).
- Any participant reporting onset of a possible symptom of COVID-19 or a possible exposure to SARS-CoV-2 should trigger an Unscheduled Visit (Section 4.5.3.7) for further evaluation. This visit should ideally occur within 72 hours of COVID-19 symptom onset or reported SARS-CoV-2 exposure. Should the participant manifest symptoms within the first 4 days after each vaccination, refer to Section 4.5.3.7 for further consideration.

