7.4.1.1.4 Medically Attended Adverse Events

An MAAE is an AE that leads to an unscheduled visit (including a telemedicine visit) with a healthcare provider (HCP, eg, nurse, nurse practitioner, physician's assistant, physician). This would include visits to a study site for unscheduled assessments (eg, rash assessment, possible COVID-19 symptoms, and visits to HCPs external to the study site for acute changes in health (eg, urgent care, primary care physician). Investigators will review unsolicited and solicited AEs for the occurrence of any MAAEs. If a solicited AE leads to an unplanned HCP visit for evaluation of the symptoms, this will be entered as an unsolicited AE (also marked as an MAAE) in addition to the solicited AE captured. The following considerations of MAAEs also apply:

- Routine study visits will not be considered medically attended visits.
- AEs observed in the immediate 30-minute post-vaccination observation period will be regarded as an MAAE if:

- Treatment of the AE is required prior to discharge OR
- Extension of observation is required due to clinical concerns or unstable clinical findings

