7.4.1.1.7 Cases of COVID-19 or Asymptomatic SARS-CoV-2 Infection

Onset of symptoms (eg, respiratory tract infection) suggestive of COVID-19 may first be reported by sites as an AE or SAE. As reflected in other sections of the protocol, symptoms suggestive of COVID-19 should be evaluated promptly for virological confirmation of SARS-CoV-2 virus. In addition, should further evaluation of the clinical case determine that the case is virologically confirmed COVID-19 or asymptomatic SARS-CoV-2, these infections must be reported to the Sponsor within 24 hours.

All events that meet the definition of an SAE will be captured as SAEs, regardless of whether they are regarded as COVID-19-related events.

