7.4.1.3 Reporting Adverse Events

Non-serious unsolicited AEs are recorded through 28 days after study vaccine administration, unless they meet the protocol definition of MAAE, SAE, or AEs leading to withdrawal/discontinuation, which will be recorded and reported for the duration of study participation.

All unsolicited AEs reported or observed during the study will be recorded on the AE page in the eCRF. Information to be collected includes the following:

- event term
- date of onset
- date of resolution/stabilization
- for AEs occurring within 24 hours of the vaccination only: time of onset
- investigator-specified assessment of severity and relationship to the study vaccine or study procedure
- for AEs initiating and resolving within 24 hours of the vaccination only: time of resolution of the event
- seriousness
- any required treatment or evaluations
- outcome
- whether the AE met the protocol definition of MAAE
- whether the AE led to study vaccine withdrawal

Adverse events resulting from concurrent illnesses, reactions to concurrent illnesses, reactions to concurrent medications, or progression of disease states must also be reported. All AEs (solicited and unsolicited) will be followed to adequate resolution. The Medical Dictionary for Regulatory Activities (MedDRA) dictionary will be used to code all unsolicited AEs.

Any medical condition that is present at the time that the participant is screened but does not deteriorate should be reported as medical history rather than as an AE. However, if this medical condition deteriorates at any time during the study, it should be recorded as an AE.

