#### 6.6.1.2 Unsolicited Adverse Events

Unsolicited AEs are defined as any spontaneously reported or discovered AE. Unsolicited AEs can also be solicited AE that leads to: A medically attended visit, an SAE, a discontinuation of study vaccine, a withdrawal from the study, or any solicited AE that persists beyond 7 days after the first study vaccine administration.

Unsolicited AEs will be coded using the MedDRA and displayed in tables using System/Organ/Class (SOC) and Preferred Term (PT). Treatment emergent AEs will be presented in tables, and all AEs will be included in listings where applicable.

In any tabulation, unsolicited AEs will be summarized by participant, therefore, a participant contributes only once to the count for a given Unsolicited AE (SOC or PT) in the tabulation. All episodes of all events will be provided in listings.

Unsolicited AEs with onset during the first 28 days after vaccination will be analyzed in the following analysis sets as defined below:

Analysis set	Timepoint
Phase 1/2/3a SAS	

After Dose 1, after Dose 2, after Dose 1 or 2

After Dose 3, after Dose 4

After Any dose

Phase 3b SAS	

After Dose 1, after Dose 2, after Dose 1 or 2

After Dose 3, after Dose 4

After Any dose

Phase 3c SAS	

After Dose 1, after Dose 2, after Dose 1 or 2

	• After Any dose
Pooled SAS	• After Dose 1, after Dose 2, after Dose 1 or 2
	• After Dose 3, after Dose 4
	• After Any dose

Participants will be considered for the computation of percentages in the specified time interval if they received the study vaccine in the specified interval. For each time interval the number of participants without missing dose will be presented.

Only data up to receipt of non-study COVID-19 vaccine (IcEv2) will be included in summary tables. Participant's data after the receipt of non-study COVID-19 vaccine will be summarized separately in a similar manner as unsolicited AEs for the following time interval: from the receipt of non-study COVID-19 vaccine up to the Final Visit/ET.

The following summaries will be presented for unsolicited AEs:

- Overview of number and percentage of participants with at least one:
  - AE
  - Related AE
  - AE by severity
  - MAAE
  - Related MAAE
  - SAE
  - Related SAE
  - AE leading to premature discontinuation of vaccine series

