  - AE leading to withdrawal from study
  - AE with death as an outcome
  - AE with covid-related death as an outcome
- Number and percentage of participants with an AE by SOC and PT
- Number and percentage of participants with an AE by PT sorted by descending frequency in the ARCT-154 group
- Number and percentage of participants with an AE related to study vaccination by SOC and PT
- Number and percentage of participants with an AE by SOC, PT and severity
- Number and percentage of participants with an AE related to study vaccination by SOC, PT and severity

Overview tables and outputs by SOC and PT after each will be also produced by subgroups as specified in Section 6.2.5 based Phase 3b SAS.

Non-treatment emergent AEs will be listed.

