### 9.2.3 Estimands for Primary Safety Analyses for Phase 1/2/3a, Phase 3b, Phase 3c and Pooled Cohorts

Estimand Label	Estimand 3 (Safety – Unsolicited AEs/AEs leading to discontinuation or withdrawal/MAAE/SAE)
Estimand Description	
Count and percentage of vaccinated participants who would develop unsolicited AEs, AEs leading to discontinuation/withdrawal, MAAEs, and SAEs.
 
These will be evaluated with each dose of study vaccine, ARCT-154 or placebo.

Target Population	The population who are enrolled in the study and receive any dose of study vaccine

Endpoint	Occurrence of unsolicited AEs will be analyzed up to 28 days after each study vaccine administration.  Occurrence of AEs leading to discontinuation/withdrawal, MAAEs, or SAEs will be analyzed up to Day of Switchover/Further Study Vaccine, receipt of non-study vaccine, early withdrawal, or last on-study assessment visit, whichever comes first.  Occurrence of AEs leading to discontinuation/withdrawal, MAAEs and SAEs after the Switchover/Further Study Vaccine will be recorded and summarized for the interval from the switchover/Further Study Vaccine up to Day 394 (Phase 1/2/3a and Phase 3b only).  For Phase 1/2/3a and 3b, AEs in participants who do not undergo Switchover/Further Study Vaccine will be recorded for the interval from Day 92 up to Day 394
Treatment Conditions	Phase 1/2/3a and 3b: ARCT-154 dose 5 µg or placebo administered on Day 1, Day 29, or at Switchover/Further Study Vaccine (Day 92 and Day 120)  Phase 3c: ARCT-154 dose 5 µg or ChAdOx1 administered on Day 1 and Day 29.
Population-Level Summary	Percentage of vaccinated participants who develop each type of AE
Intercurrent Event (IcEv) Strategy	
IcEv1 (Death not due to COVID-19)	Composite strategy
IcEv2 (Non-study vaccine)	While on treatment strategy
IcEv3 (Early infection)	Composite strategy

IcEv4 (Study infection)	Composite strategy
IcEv5 (Confounding On-study Medications)	treatment policy strategy
Rationale for Strategies	Events occurring after IcEv2 could contribute spurious safety data so a while on treatment policy is used for these events and events occurring after this IcEv's will be summarized separately.
Estimand Label	Estimand 4 (Reactogenicity – Solicited AEs)
Estimand Description	Count and percentage of vaccinated participants who would develop solicited AEs. These will be evaluated after vaccination on Day 1 and Day 29, ARCT-154 or placebo.

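### The overall AE, MAAE and SAE rates count COVID-19 and no rate without it is planned, so efficacy up to Day 92 can offset an excess of other events, chiefly among MAAEs

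*Protocol*

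**What the plan says.** Protocol Section 8.7.2, Table 18, sets the rule for Estimand 3: "SARS-CoV-2 infections and death due to COVID-19 (if they meet the AE and time window criteria) are included in the endpoint (composite strategy". SAP Section 9.2.3 repeats it, giving "Composite strategy" for both early infection (IcEv3) and study infection (IcEv4).

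The event definitions bring COVID-19 in by several routes:

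- **MAAEs.** Protocol Section 7.4.1.1.4 counts unplanned healthcare visits: "This would include visits to a study site for unscheduled assessments (eg, rash assessment, possible COVID-19 symptoms". Section 4.5.5.2 makes such visits routine: "Any participant reporting onset of a possible symptom of COVID-19 or a possible exposure to SARS-CoV-2 should trigger an Unscheduled Visit".
- **SAEs.** Protocol Section 7.4.1.1.7: "All events that meet the definition of an SAE will be captured as SAEs, regardless of whether they are regarded as COVID-19-related events".
- **Window.** Protocol Section 7.4.1.3: "Non-serious unsolicited AEs are recorded through 28 days after study vaccine administration". MAAEs and SAEs are recorded for the whole of participation.

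On the output side, SAP Section 6.6.1.2 states one cut-off: "Only data up to receipt of non-study COVID-19 vaccine (IcEv2) will be included in summary tables". Infection is not a cut-off there. The only overview row that singles out COVID-19 is "AE with covid-related death as an outcome". The SAP also plans SOC/PT tables, related-only tables (Sections 6.6.1.2 and 6.6.1.3) and frequency tables of adjudicated COVID-19 cases for Day 1-35 and Day 36-92, including in the ITT set (Section 6.4).

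SAP Section 7.3 says something different about Estimand 3: only events before a non-study vaccine or before early COVID-19 infection enter the analysis.

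**The concern.** The Phase 3b safety endpoints are the study's overall primary safety endpoints (Protocol Section 8.4.2; SAP Section 6.2.3). Because infection counts as a safety event, the efficacy outcome sits inside them. If the vaccine works, placebo accumulates more COVID-19 MAAEs and SAEs, and the overall rows show a balance, or an advantage, to which efficacy has contributed.

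The composite rate answers a legitimate question: the net burden of events. It does not answer whether the vaccine causes other events. An excess spread thinly over many terms, and not attributed to the vaccine by investigators, is what an overall row should reveal. Here that row carries an offset of predictable direction, and no COVID-free counterpart is planned.

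**Working it through.** **Inputs from the documents.** 372 cases, 50% efficacy tested against a 30% null, one-sided 0.025, about 90% power, 1:1 allocation (Protocol Sections 8.4.2 and 8.5.2); about 8,000 per arm in Phase 3b (Section 8.5.2); case onset Day 36 to Day 92 (Section 3.2.1).

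**Assumptions not in the documents.** Non-COVID MAAE background b of 2%, 5% or 10%; share of cases entered as MAAEs 50% or 100%; share of cases that are SAEs 2% to 20%; non-COVID SAE background 0.3% to 1%; COVID-19 and other events independent; 8,000 used as the denominator.

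**Step 1: reproduce the plan's figure.** Schoenfeld's formula with hazard ratio 0.5/0.7: events = 4 × (1.960 + 1.282)² / [ln(0.714)]² = 42.03 / 0.1132 = 371.2, rounded up to 372. Power at 372 is 90.06%. The plan's figure reproduces.

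**Step 2: split the cases.** With few cases relative to 8,000, placebo cases ≈ 372 / (2 − 0.5) = 248 and ARCT-154 cases ≈ 124. Risks are c0 = 248/8,000 = 3.10% and c1 = 124/8,000 = 1.55%. The gap is 124 participants, or 1.55 points. For the same 372 cases it would be 0.82 points at 30% efficacy and 2.50 at 70%.

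**Step 3: find the excess that disappears.** With e the vaccine-caused excess of non-COVID MAAEs, the all-cause risks are:

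- ARCT-154: 1 − (1 − b − e)(1 − c1)
- Placebo: 1 − (1 − b)(1 − c0)

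Setting them equal gives e = (1 − b)[1 − (1 − c0)/(1 − c1)]. With all cases entered, the bracket is 1 − 0.9690/0.9845 = 0.01574. With half entered, it is 1 − 0.98450/0.99225 = 0.00781.

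| Background b | Hidden excess, all cases entered | Power to see it if COVID-19 is excluded | Hidden excess, half entered |
|---|---|---|---|
| 2% | 1.54 points (123 participants) | about 100% | 0.77 points |
| 5% | 1.50 points (120) | 98% | 0.74 points |
| 10% | 1.42 points (113) | 83% | 0.70 points |

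Power is for a two-sided 5% comparison of two proportions, 8,000 per arm.

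**Step 4: worked example.** Take b = 5% and a true excess of 1 point (6.0% v 5.0%, ratio 1.20; 79% power if COVID-19 is excluded).

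- All cases entered: ARCT-154 1 − 0.94 × 0.9845 = 7.46%; placebo 1 − 0.95 × 0.9690 = 7.95%. The ratio is 0.94, so the direction reverses.
- Half entered: 6.73% v 6.47%, ratio 1.04. The excess shrinks but keeps its sign.

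**Step 5: SAEs.** If 2% to 20% of cases are SAEs, at the same proportion in both arms, the hidden excess runs from about 2.5 to 25 participants (0.03 to 0.31 points). Over most of that range a COVID-excluded comparison would also have little power.

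**Step 6: where the figures apply.** The 28-day window after Dose 2 closes at about Day 57 (29 + 28), whereas the 372 cases run to Day 92. The figures therefore describe MAAEs and SAEs to Day 92, not 28-day unsolicited AEs. Cases in Day 1-35 would add to them.

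**The case against.** The strongest case against is that COVID-19 is not wholly buried, and much of this case stands.

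- PT rows count participants within the row, so an excess in a non-COVID term, or in an SOC holding no COVID-19 events, shows directly. Masking is confined to the overall rows and to the SOCs that hold COVID-19 or its symptoms.
- Related-only tables remove cases judged unrelated, as far as investigator causality can be trusted.
- The adjudicated case tables in ITT show the imbalance in a set with the same membership criterion as the SAS.
- Table 18 makes inclusion conditional, and suspected cases also go onto dedicated eCRF pages (Protocol Section 4.5.3.7), so not every case need become an MAAE. Hence the half-entered column.
- Safety has no hypothesis test, and the DSMB sees unblinded data. No formal decision turns on the affected rows.

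A reader might therefore infer too much in two ways. One is that no planned output separates COVID-19 except for deaths; the tables above show otherwise. The other is a sizeable SAE effect obtained by treating severe COVID-19 as an SAE. The documents give no serious share, and the severity criteria in Protocol Appendix 2 differ from the SAE criteria in Section 7.4.1.1.2.

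What the objection does not supply is a COVID-free participant total. One participant can have several terms, so PT rows cannot be summed or subtracted to reach it. A case may also first be reported as symptoms (Protocol Section 7.4.1.1.7), so a COVID-19 term row need not hold every case.

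**Conclusion.** The concern holds in this form: COVID-19 counts in the overall AE, MAAE and SAE rates, no overall or SOC-level rate without it is planned, and the outputs that separate it do so only in part. The offset favours the vaccine in the placebo-controlled period to Day 92 in Phases 1, 2, 3a and 3b. Phase 3c has an active comparator, so no direction can be stated there.

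For MAAEs the effect is large enough to matter at the plan's own case count and efficacy. It can cancel a real excess, and in the worked example with all cases entered it reverses one. The exact size rests on the assumed background and on the share of cases entered. For SAEs the offset is probably small, and the documents do not allow it to be fixed. The documents do not support a claim that the trial's safety conclusion would be wrong; they support the claim that one set of primary summaries is predictably tilted and has no companion that corrects it.

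There is also a plain inconsistency. SAP Section 7.3 stops counting at early infection, while SAP Section 9.2.3 uses a composite strategy for it and Section 6.6.1.2 cuts only at non-study vaccine. Section 7.3 describes its rule as a return to the protocol, yet Protocol Table 17 also gives a composite strategy for early infection. Applying Section 7.3 would still leave participants first infected from Day 36 onward in the rates.

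**What to change.** Keep the composite tables. In SAP Sections 6.6.1.2 and 6.6.1.3 add, for the Phase 3b, Phase 1/2/3a and Pooled SAS up to Day 92 or Switchover, the same overview and SOC/PT tables of unsolicited AEs, MAAEs and SAEs with COVID-19 events excluded. Define the excluded events as COVID-19 or SARS-CoV-2 preferred terms, plus any AE that the case record links to a virologically confirmed infection, so that symptom-coded events are covered. Label the tables non-COVID-19. They should not be described as free of reactogenicity, because solicited events that lead to a medical visit, become serious or persist are re-entered as unsolicited AEs (Protocol Section 7.4.1.1.1.1; SAP Section 6.6.1.2).

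Reconcile SAP Section 7.3 with Sections 9.2.3 and 6.6.1.2, so that a single rule says whether events after early infection are counted.

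The cost is one derived flag and one extra set of tables.
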